## 9.0 Sample Size and Eligibility Criteria

### 9.1 ENROLLMENT TARGET: How many people will you enroll:

If there are multiple participant groups, indicate how many people will be in each group:

A total of 50 participants will be enrolled into this study. 40 participants with cLBP will be enrolled into 4 consecutive MBPR classes ( $n = 10$  for each course). 10 participants with cLBP will be in the MBSR as the control group.

Specifically, the first 30 participants of the total 50 enrolled in the study will be assigned to MBPR classes and the final 20 participants will be randomly assigned to MBSR ( $n = 10$ ) or to MBPR ( $n = 10$ ) to test recruitment and randomization approaches.

**9.3 SAMPLE SIZE JUSTIFICATION: Explain how and why the number of people was chosen. For multi-site studies, this is referring to the number that will be enrolled across all sites:**

The primary goal of this study is to prepare for a rigorous RCT comparing efficacy of the MBPR intervention to alternatives. We are not aiming to test efficacy in the current study and do not have adequate sample size for this assessment. The proposed sample sizes were selected based on the numbers we estimate will be needed to adequately refine the intervention and assess its acceptability and feasibility, and to obtain variance estimates to inform future work. However, we will conduct **exploratory analyses** to obtain estimates of ICCs of the repeated measures from linear mixed models, and run linear mixed models with pain as outcome, and an interaction between study period and psychological variables (e.g. PCS-SF, FABQ-PA, and MAIA-2) as predictors, with nested random effects of person nested within class group. Although using all participants across all iterations of MBPR is limited by variations in the intervention, with a total MBPR sample size of 40 (out of 50 total enrolled, with a control/MBSR group of  $n = 10$ ), we will have 80% power (two-tailed alpha = 0.05) to detect a statistically significant correlation if the expected coefficient of determination is 0.43 or greater.

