### 6.2 Justification of Sample Size

The primary goal of this study is to prepare for a rigorous RCT comparing efficacy of the MBPR intervention to alternatives. We are not aiming to test efficacy in the current study and do not have adequate sample size for this assessment. The proposed sample sizes were selected based on the numbers we estimate will be needed to adequately refine the intervention and assess its acceptability and feasibility, and to obtain variance estimates to inform future work. However, we will conduct **exploratory analyses** to obtain estimates of ICCs of the repeated measures from linear mixed models, and preliminary estimates looking at Pearson correlations between changes in pain outcomes and changes in psychometric scale measures that we understand to be potential mediators of change in pain intensity following mindfulness interventions, e.g. PCS-SF, FABQ-PA, and MAIA-2. Although using all participants across all iterations of MBPR is limited by variations in

the intervention, with an exploratory total MBPR sample size of 40, we will have 80% power (two-tailed alpha = 0.05) to detect a statistically significant correlation if the expected Pearson correlation coefficient comparing change scores for pain outcomes with change scores for psychometric scale measures is 0.43 or greater. If we experience a loss to follow-up rate of 10% in our classes, the sample size per subsequent class will be increased to 11 subjects.

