Hypothesis 4: Assessment of pain intensity/interference with a smartphone delivered EMA is feasible and correlates with standard pain outcome measures. Feasibility/acceptability measures are noted in the table above. We will assess the correlation of our EMA measures with the Numeric Pain Rating Scale for pain intensity, and pain interference rating. We predict a correlation of >.7. We will also perform qualitative assessment to get participants assessment of where the two approaches are similar, and where they may get differing responses.

Hypothesis 5: Assessment of meditation practice adherence is feasible using a smartphone app. At the 8-week assessment period, we will include questions about meditation practice over the prior week and compare this with the results from use of the Meditation Insight Timer data. We will ask further questions about any sessions that were not recorded using the app, and reasons for not recording. This information will be analyzed after each group, and refinements made if needed in participant instructions and other steps to encourage use of the app as consistently as possible.

Hypothesis 6: We will conduct **exploratory analyses** to test for correlations between changes in pain outcomes and scores on the PCS, TSK, CPAQ, MAIA, and FFMQ using regression models.

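### SAP Hypothesis 6 leaves the type and visit of the scale score open, and it does not match the change-against-change analysis in DSMP 6.2 or the model in Protocol 9.3

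*SAP*

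**What the plan says.** Three places describe an exploratory analysis linking pain to psychological scales.

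- **SAP, Hypothesis 6:** the analysis will "test for correlations between changes in pain outcomes and scores on the PCS, TSK, CPAQ, MAIA, and FFMQ using regression models". No visit is named for the scores. No covariates, sample, effect size or power are given. The SAP's overall approach says that significance is not expected and that effect sizes will be estimated.
- **DSMP 6.2 (inside Protocol 13.1):** the analysis is "Pearson correlations between changes in pain outcomes and changes in psychometric scale measures", with the scales presented as possible mediators. Power of 80% at a two-sided alpha of 0.05 is claimed for the 40 MBPR participants "if the expected Pearson correlation coefficient comparing change scores for pain outcomes with change scores for psychometric scale measures is 0.43 or greater".
- **Protocol 9.3:** a linear mixed model with pain as outcome and "an interaction between study period and psychological variables (e.g. PCS-SF, FABQ-PA, and MAIA-2) as predictors". The same 0.43, 80% and n = 40 appear, but 0.43 is called a coefficient of determination.

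Protocol 7.9 schedules questionnaires in the first and last week of the course, with clinical outcomes again at 6 months. The instrument list in Protocol 7.11 includes short forms of the PCS and CPAQ, the MAIA and the FFMQ, none marked as baseline only. It includes FABQ-PA. It does not include TSK, which Hypothesis 6 names.

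**The concern.** The three descriptions do not estimate the same thing. A change score asks whether the proposed mechanism moved together with pain. A baseline score asks who responds. An 8-week score mixes the two. Under the SAP sentence an analyst could enter any of them and claim to have followed the plan.

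Two consequences follow. First, the only power statement that fits a correlation belongs to change against change and does not carry over to a level. Second, an unadjusted level can correlate with pain change for reasons unrelated to mediation. People with worse pain at baseline tend to regress towards the mean, and any scale correlated with baseline pain inherits part of that association. The study is meant to prepare a larger trial, so a mislabelled mechanism estimate could be carried into its design.

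**Working it through.** **1. The plan's own figure.** Inputs from DSMP 6.2: r = 0.43, n = 40, two-sided alpha 0.05. Fisher z: atanh(0.43) = 0.4599; times sqrt(40 - 3) = 6.083 gives 2.797; power = Phi(2.797 - 1.960) = 79.9%. Adding the small-sample term r/(2(n - 1)) gives 80.8%, and simulation of the t test of r gives 80.9%. The stated 80% reproduces as a Pearson r. With 36 completers (10% loss and no enlargement of later classes) it is 75-76%.

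**2. The label in Protocol 9.3.** If 0.43 were R-squared, r = sqrt(0.43) = 0.656 and power at n = 40 would be 99.8%. So the 80% belongs to r = 0.43, which is R-squared = 0.43^2 = 0.185.

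**3. What a level would estimate (illustration).** Let S1 and S2 be the scale at baseline and 8 weeks, with equal SDs and correlation rho. Assume that pain change relates to the scale only through S2 - S1. Then

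corr(S2 - S1, S2) = (1 - rho)/sqrt(2(1 - rho)) = sqrt((1 - rho)/2),

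and corr(S2 - S1, S1) is the same with a minus sign. So the correlation of pain change with either level has size 0.43 * sqrt((1 - rho)/2), with opposite signs for baseline and 8 weeks. No document gives rho, so it is varied. Power is at n = 40, two-sided 0.05:

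| rho (assumed) | size of r | Fisher z | with small-sample term |
|---|---|---|---|
| 0 | 0.304 | 48% | 49% |
| 0.3 | 0.254 | 35% | 36% |
| 0.5 | 0.215 | 26% | 27% |
| 0.6 | 0.192 | 22% | 22% |
| 0.7 | 0.167 | 18% | 18% |
| 0.8 | 0.136 | 13% | 13% |
| 0.9 | 0.096 | 9% | 9% |

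If a level itself correlated 0.43 with pain change, power would again be about 80%. Power depends on the size of the correlation, not on whether the predictor is a level or a change.

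**4. Confounding by baseline pain (illustration).** Suppose there is no mediation. The baseline scale correlates c with baseline pain, 8-week pain depends only on baseline pain with pre-post correlation p, and the pain SDs are equal. Then corr(pain change, baseline scale) = -c * sqrt((1 - p)/2). Neither c nor p is in the documents. For p = 0.6, c = 0.3 gives -0.134 and c = 0.5 gives -0.224. The unadjusted test at n = 40 is then significant about 13% and 29% of the time, against a nominal 5%. For p = 0.8 the same c values give about 9% and 16%. Adjusting for baseline pain removes this effect in this model.

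**The case against.** A reader might infer that Hypothesis 6 definitely tests levels, that its power is 13-27%, that the direction of the result would be reversed, and that a power figure in the SAP is wrong. The documents do not support that.

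- **Grammar.** The phrase about changes can be read as covering both pain outcomes and scores. DSMP 6.2 spells out that meaning. A level is the more literal reading, but what is certain is only that the score type and visit are unspecified.
- **The power range.** It rests on three assumptions found in no document: the pre-post correlation, equal variances, and dependence on change only. The sign reversal rests on the last two of these.
- **Regression.** The SAP says regression models. If the baseline score is in the model, the test of the 8-week score is algebraically the same as the test of the change. The loss applies only to a model without it. The SAP names no covariates, so this cannot be settled.
- **No power claim.** The SAP states none for Hypothesis 6, calls it exploratory and does not expect significance. No feasibility conclusion depends on it.
- **Baseline predictors.** Who responds is a legitimate question; neuroimaging Aim 1 in Protocol 7.2 asks it of attention style.

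All of this stands, and it limits the point to a minor one. It does not remove it. The sentence has more than one compliant analysis, and the SAP, DSMP 6.2 and Protocol 9.3 describe the exploratory analysis in three forms. Reporting estimates instead of p-values does not help if it is unclear which quantity is being estimated. The SAP carries the earliest date of the dated texts (2019, against 2020 for the DSMP), so it may simply not have been updated.

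**Conclusion.** The concern holds in limited form, and its severity is minor. Hypothesis 6 leaves the type and visit of the scale score open and, read literally, uses a level. DSMP 6.2 specifies change against change, and its 80% is correct for that unadjusted Pearson correlation and for nothing else. Protocol 9.3 gives a further model and mislabels 0.43.

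The numerical consequence is conditional: power of about 13-27% for a level if the pre-post correlation is 0.8-0.5, and 9-49% over 0.9-0, under the assumptions in step 3 of the working. These figures show why the choice matters. They are not an estimate of this study's power.

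**What to change.** 1. In SAP Hypothesis 6, state that change in each pain outcome from baseline to 8 weeks is regressed on change in each scale over the same interval, adjusting for baseline pain and baseline scale score.
2. If baseline scores are of interest as predictors of response, list that as a separate exploratory analysis.
3. Attach 0.43 and 80%, labelled as a Pearson r, only to the unadjusted change-change correlation of DSMP 6.2. The baseline-adjusted regression in item 1 is a different analysis, and the figure does not carry over to it either.
4. Align Protocol 9.3, DSMP 6.2 and SAP Hypothesis 6 on one primary form of this exploratory analysis, and correct the coefficient label in Protocol 9.3.
5. Reconcile the scale list. TSK is in the SAP but not in Protocol 7.11, which has FABQ-PA; DSMP 6.2 and Protocol 9.3 name PCS-SF, FABQ-PA and MAIA-2 as examples.

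The cost is a few sentences. Four of the five scales named in Hypothesis 6 are already planned at both visits. TSK would have to be dropped, replaced or added to the instruments.
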